4.6.1.4 Immunogenicity

4.6.1.4.1 Definitions

4.6.1.4.1.1 ADAb sample status (positive, negative, missing)

The ADAb sample results will be provided as “Positive Screen” (PS) or “Negative Screen” (NS). For samples presenting ADAb levels that are PS, a further confirmatory assay will be performed, and the result will be reported as either “Positive Immunodepletion” (PI) or “Negative Immunodepletion” (NI).

The ADAb status for each sample will be derived as follows:

- Sample values that are either NS, or PS and NI and where the bimekizumab concentration is less than the validated ADAb assay drug tolerance limit ($200\mu\text{g/mL}$) will be defined as ADAb-negative. Since the bimekizumab concentration is not collected at the SFU visit, the ADAb status will be defined as ADAb-negative if the ADAb sample values are either NS, or PS and NI at the SFU visit.
- Sample values that are either NS, or PS and NI and where the bimekizumab concentration exceeded the validated ADAb assay drug tolerance limit will be defined as inconclusive. Since the bimekizumab concentration is not collected at the SFU visit, the ADAb status will be defined as ADAb-negative if the ADAb sample values are either NS, or PS and NI at the SFU visit.
- Sample values that are PS and PI will be defined as ADAb-positive (regardless of availability of a titer value).
- Missing or non-evaluable samples will be defined as missing.

The PI samples will be titrated and the ADA_b titer (reciprocal dilution factor including minimum required dilution) will be reported. The PI samples will also be analyzed in a neutralizing assay to evaluate the anti-bimekizumab antibody neutralized target binding of bimekizumab (IL-17AA or IL-17FF or both) in vitro.

4.6.1.4.1.2 Cumulative ADA_b status

The ADA_b status (positive, negative, or missing) will be considered in a cumulative manner at each time point.

A study participant will be counted positive from the first visit at which the study participant achieved a positive ADA_b sample result to the end of the treatment period, regardless of any missing/inconclusive or negative ADA_b sample result.

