- **Pre ADA_b negative – treatment emergent ADA_b positive (Category 2):** Includes study participants who are ADA_b negative at Baseline and ADA_b positive at any sampling point post treatment (including SFU). This group also includes study participants who have a missing pre-treatment sample (either missing or insufficient volume) at Baseline with one or more ADA_b positive post-treatment samples.
- **Pre ADA_b positive – treatment emergent reduced ADA_b (Category 3):** Includes study participants who are ADA_b positive at Baseline, and ADA_b negative at all sampling points post treatment (including SFU).
- **Pre ADA_b positive – treatment emergent unaffected ADA_b positive (Category 4):** Includes study participants who are positive at Baseline and are positive at any sampling point post treatment (including SFU) and all post-Baseline samples have titer values <2.07 times the Baseline titer (where 2.07 is Minimum Significant Ratio [MSR]).
- **Pre ADA_b positive – treatment boosted ADA_b positive (Category 5):** Includes study participants who are positive at Baseline and have at least one post-treatment sample (including SFU) that has titer value ≥ 2.07 times the Baseline titer (where 2.07 is MSR).

Note: For any study participant who is positive at Baseline and positive at a post-Baseline time point, but for whom titers are not available to determine treatment unaffected or treatment boosted status, the study participant will be considered as treatment boosted (ie, Category 5), assuming no other samples are available.
- **Inconclusive (Category 6):** Includes study participants who have a positive pre-treatment sample and some post-treatment samples are missing/inconclusive, while other post-treatment samples are ADA_b negative.
- **Total treatment-emergent (Category 7 [Categories 2 and 5 combined]):** Includes study participants who are pre ADA_b negative – treatment emergent ADA_b positive (Category 2) and pre ADA_b positive – treatment boosted ADA_b positive (Category 5).
- **Total prevalence of pre-ADA_b positivity (Category 8 [Categories 3, 4, 5, and 6 combined]):** Study participants that are tested ADA_b positive at Baseline.

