- **Missing (Category 9):** Includes study participants who have a negative or missing/inconclusive pre-treatment sample at Baseline and more than one post-treatment samples that are missing/inconclusive, while other samples are ADA_b negative. Also includes study participants who have a missing/inconclusive pre-treatment sample at Baseline, and only one missing post-Baseline sample with no ADA_b-positive.

4.6.1.4.1.5 ADA_b status groups for efficacy endpoint summaries

For the efficacy endpoint by ADA_b summaries (described below), the following ADA_b-efficacy status groups are defined:

- **ADA_b-positive** - Defined as study participants having at least 2 ADA_b-positive samples up to the time point of interest (ie, excluding Baseline, excluding SFU) regardless of other ADA_b-negative samples and/or missing or inconclusive samples

- ADAb-negative - Defined as study participants for whom either
 1. all samples to the time point of interest are ADAb-negative and there are no missing or inconclusive samples,
 2. only one sample is ADAb-positive and all other to the time point of interest (including Baseline) are ADAb-negative or missing/inconclusive, or
 3. only one sample is missing/inconclusive and the remaining ADAb samples are negative.
- Missing - Defined as study participants who do not fulfil the criteria for one of the 2 groups listed above.

The ADAb data from Baseline up to the time point of interest will be used to derive the ADAb-efficacy status groups.

The rationale for requiring at least 2 time points in which the participant is confirmed positive is to exclude individuals who have only one occurrence of ADAb levels during the period of interest. Including such study participants would increase the number of ADAb-positive participants with potentially no impact on efficacy.

4.6.1.4.1.6 Neutralizing anti-bimekizumab antibodies (NAb) categories

The NAb will be assessed using IL-17AA- and IL-17FF- specific assay methods, respectively. A NAb result will be positive or negative to each specific NAb assay or both.

Any NAb results derived from samples with drug concentrations higher than the drug tolerance limits of the NAb assays (100µg/mL) will be labeled 'inconclusive'. All inconclusive results will be regarded as missing.

Study participants will be assigned an overall NAb classification, inclusive of Baseline and post-Baseline results from NAb assay:

- NAb negative:

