 - ADAb positive / NAb negative: No NAb positive samples for IL-17AA and IL-17FF at Baseline or post-Baseline. This group also includes study participants who have only one missing sample and all other available samples during the period of interest are negative.
 - ADAb negative: negative samples (refer to Section 4.6.1.4.1.3) are not analyzed for NAb.
- NAb positive: One or more positive samples (IL-17AA positive, IL-17FF positive, or both) at Baseline or post-Baseline (regardless of missing samples). Study participants who are NAb positive will be further classified as follows:
 - Positive for IL-17AA only: one or more positive samples for IL-17AA at Baseline or post-Baseline (and no samples are positive for IL-17FF).
 - Positive for IL-17FF only: one or more positive samples for IL-17 FF at Baseline or post-Baseline (and no samples are positive for IL-17AA).
 - Positive for both IL-17AA and IL-17FF: one or more positive samples for both IL-17AA and IL-17FF at Baseline or post-Baseline.

- NAb Missing: more than one relevant NAb samples are missing/inconclusive and other available NAb samples during the period of interest are negative, eg, missing or insufficient sample left for NAb testing.

4.6.1.4.1.7 ADAb Sample Inclusion and Exclusion Rules

The following rules will be implemented for by-visit ADAb summaries if applicable:

- If the ADAb sample is collected within ± 14 days (excluding the Week 32, PEOT, or SFU visit) relative to the visit date at which the IMP was administered, the ADAb result for that sample will be associated with the scheduled visit and summarized accordingly.
- In all cases, this will include unscheduled assessments (if a dose was administered at an unscheduled visit).

Samples collected outside the relevant windows described above will be excluded from the ADAb by-visit summaries and will be listed only.

For samples associated with the Week 32, PEOT, or SFU, all ADAb data obtained will be included in the by-visit summaries.

All other summaries of ADAb (as described in the following sections) will use all available (both scheduled and unscheduled) data.

The reason for exclusion will be assigned as one or more of the following:

- Sample collected out of window relative to current dose (or visit)
- More than one sample obtained at the same visit

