- Number and percentage of PASI90 responders at Week 16 and Week 32 as a function of Week 16 and Week 32 ADAb titer categories (categorized as ≤ 100 [at or below the MRD of the assay], $>100 - < \text{median}$ [of non-missing titer values >100], and $\geq \text{median}$ [of non-missing titer values >100]). This will be repeated for IGA 0/1 responders at Week 16 and at Week 32. These data will also be presented graphically (for the figure, any study participant with ADAb-positive/ADAb titer missing is included ≤ 100 group).
- Individual plots of bimekizumab concentrations, ADAb titer, and PASI90 response (based on NRI) will be created. All 3 endpoints will be plotted on the Y-axes by time (X-axis) for the full treatment period including SFU. Plots will be labeled and grouped into the 7 predefined ADAb categories (category 1, 2, 3, 4, 5, 6, and 9).

The following summaries of NAb data will be prepared by treatment group:

- Number and percentage of PASI90 responders at Week 16 and at Week 32, by NAb category (ADAb-negative, NAb-positive, ADAb-positive / NAb-negative). This will be repeated for IGA 0/1 responders. These data will also be presented graphically.
- Number and percentage of PASI90 responders over time (up to Week 16 and Week 32) separated by NAb category (ADAb-negative, NAb-positive, ADAb-positive/NAb negative). This will be repeated for IGA 0/1 responders (up to Week 16 and Week 32). These data will also be presented graphically.

4.6.1.4.2.4 Safety endpoints by ADAb and NAb summaries

Summaries include the number of TEAEs, number of study participants with TEAEs, percentage of study participants with TEAEs, EAIR with 95% CI, and EAER. TEAEs will be sorted by SOC, HLT and PT.

TEAEs by ADAb status and ADAb titer:

TEAEs of the study participants initially randomized to bimekizumab 320mg Q4W/Q8W treatment, or initially randomized to placebo and initiating bimekizumab 320mg Q4W treatment at Week 16, will be summarized by ADAb status based on all available data using the following categories:

- AEs starting before the first ADAb-positive result (study participants in Categories 2 and 5)
- AEs starting on or after the first ADAb-positive result (study participants in Categories 2, 3, 4, 5 and 6)
- AEs for study participants who are always ADAb-negative (study participants in Category 1)

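### The NAb rules class an ADAb-positive participant whose only NAb result is absent as NAb-negative, and the efficacy-by-titer figures place missing titers in the lowest group

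*SAP*

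**What the plan says.** **Which samples are tested.** SAP 4.6.1.4.1.1 sends confirmed-positive samples on for neutralization testing: "The PI samples will also be analyzed in a neutralizing assay". Under 4.6.1.4.1.6, ADAb-negative samples are not tested. One positive sample is enough for overall ADAb-positive status (4.6.1.4.1.3).

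**How NAb status is assigned (4.6.1.4.1.6).**
- Results from samples above the 100 µg/mL drug tolerance limit are inconclusive, and "All inconclusive results will be regarded as missing".
- The negative class among ADAb-positive participants reads "ADAb positive / NAb negative: No NAb positive samples for IL-17AA and IL-17FF at Baseline or post-Baseline". It continues: "This group also includes study participants who have only one missing sample and all other available samples during the period of interest are negative".
- The missing class requires "more than one relevant NAb samples are missing/inconclusive and other available NAb samples during the period of interest are negative".

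**How a missing titer is handled.** A sample can be ADAb-positive without a titer (4.6.1.4.1.1). For the figures of PASI90 and IGA 0/1 response by titer category, 4.6.1.4.2.3 says that an ADAb-positive participant with "titer missing is included ≤ 100 group". That instruction is limited to the figure, and no rule is given for the table.

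**The concern.** The negative class asks only that no positive result exists. It does not ask that any negative result was observed. For a participant with one NAb sample, an absent result satisfies that test, while the missing class is out of reach because it needs at least two absent results.

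The SAP foresees both ingredients. In 4.6.1.4.1.5 it discusses participants with a single ADAb-positive occurrence, and in 4.6.1.4.1.6 it names insufficient sample volume as a cause of missing NAb data. For cumulative ADAb status it has an explicit rule for a lone absent Baseline sample (4.6.1.4.1.2). For NAb it has none for a lone absent result.

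At stake are the NAb incidence table (4.6.1.4.2.1) and the PK, efficacy and TEAE summaries by NAb status (4.6.1.4.2.2 to 4.6.1.4.2.4). The efficacy and TEAE summaries list only ADAb-negative, ADAb-positive/NAb-negative and NAb-positive. The label therefore decides whether an untested participant enters the comparison at all. In the titer figures, the lowest group can contain people whose titer is unknown.

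**Working it through.** The plan states no figure on this point, so there is none to reproduce. The check is to run the classification rule over every possible case.

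**Inputs.** Let k be the number of NAb samples (one per ADAb-positive sample) and m the number missing or inconclusive, with the remaining k − m negative and none positive. Protocol Table 1-1 schedules antibody samples at Baseline and Weeks 8, 16, 24 and 32 (plus SFU). So k is at most 3 up to Week 16 and at most 5 up to Week 32.

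**Rule, literal reading.** NAb Missing if m > 1; otherwise NAb-negative.
**Rule, stricter reading.** As above, but NAb-negative also needs k − m ≥ 1.
**Proposed rule.** NAb Missing if k − m = 0; otherwise as the literal rule.

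For k = 1 to 5 and m = 0 to k there are 2 + 3 + 4 + 5 + 6 = 20 cells. The informative ones are:

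| k | m | Observed negatives | Literal | Stricter | Proposed |
|---|---|---|---|---|---|
| 1 | 1 | 0 | NAb-negative | no category | NAb Missing |
| 2 | 1 | 1 | NAb-negative | NAb-negative | NAb-negative |
| 2 | 2 | 0 | NAb Missing | NAb Missing | NAb Missing |
| 5 | 2 | 3 | NAb Missing | NAb Missing | NAb Missing |

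A participant with no observed result is called negative, while one with three observed negatives and two absent results is called missing. The proposed rule changes one cell (k = 1, m = 1) and leaves the other 19 as they are. Neither reading puts that cell in NAb Missing.

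**Size (all rates assumed).** Expected number affected = n × s × q, where n is the number of ADAb-positive participants (20 to 40), s the share with a single NAb sample (25% to 50%) and q the share of those results that are absent (5% to 20%).
- Low end: 20 × 0.25 × 0.05 = 0.25 participants, or 0.25/20 = 1.25% of the ADAb-positive group.
- High end: 40 × 0.50 × 0.20 = 4 participants, or 4/40 = 10%.

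Under these assumptions the NAb-negative row is overstated, and NAb Missing understated, by 1.25 to 10 percentage points.

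**Effect on a responder rate (illustration).** Suppose 17 of 20 NAb-negative participants respond (85.0%). Adding one untested responder gives 18/21 = 85.7%; adding one untested nonresponder gives 17/21 = 81.0%. The shift is +0.7 or −4.0 points.

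**The case against.** The best defence is that the one-missing allowance presupposes other samples, so the single-sample case is merely unaddressed. The same tolerance of one missing result applies to overall ADAb status, which makes it a consistent convention. This is a fair reading, but it leaves the participant with no category, so the text still needs a sentence.

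Several larger conclusions are tempting, and the documents do not support them:

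- **That the NAb-positive percentage is understated.** The table restricted to ADAb-positive participants uses all of them as its denominator (4.6.1.4.2.1). Moving someone from negative to missing changes neither numerator nor denominator. Only a share computed among participants with an evaluable result would rise, and the SAP does not plan one.
- **That the SAP generally resolves absent antibody data favourably.** Two or more absent NAb results, with no positive, give NAb Missing. Under 4.6.1.4.1.4, when titers are unavailable for someone positive at Baseline and afterwards, "the study participant will be considered as treatment boosted (ie, Category 5), assuming no other samples are available". That rule serves incidence classification and the figure rule serves plotting, so the two do not contradict each other.
- **That the ≤100 group distorts PK or safety.** PK is summarised by ADAb and NAb status, and TEAEs by tertiles of maximum titer. The ≤100 category appears only in the PASI90 and IGA 0/1 summaries, and missing titers remain visible in the participant listing.
- **That the case will be common.** Someone first positive at Week 16 does have one NAb sample in the Week 16 table, but the documents give no ADAb incidence, no share with a single positive sample and no rate of absent NAb results.

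**Conclusion.** Wrong as written, and minor. On the literal text, an ADAb-positive participant with no NAb result is counted as NAb-negative; on the stricter reading that participant is unclassified. In the efficacy-by-titer figures, participants of unknown titer are shown in the lowest group, and the matching table is silent on them.

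The effect is confined to descriptive immunogenicity summaries, which serve a tertiary objective. The co-primary and key secondary tests are untouched. The estimate of about 0.3 to 4 affected participants rests wholly on assumed rates, and the true number may be zero. The classification finding needs none of those assumptions, because it follows from the SAP's own rules.

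**What to change.** In SAP 4.6.1.4.1.6, require at least one evaluable negative NAb result for ADAb-positive/NAb-negative. Class any ADAb-positive participant with no evaluable NAb result as NAb Missing, whatever the number of samples.

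In 4.6.1.4.2.3, replace the instruction on missing titers: either omit these participants from the figures or show them as a separate group, and state the same handling for the table.

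The cost is about two sentences of SAP wording and minor programming. The NAb Missing row becomes slightly larger. Reclassified participants leave the efficacy and TEAE summaries that list no missing group, so a footnote giving their number would help.

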4.6.1.4.2 Immunogenicity analyses

4.6.1.4.2.1 ADAb and NAb summaries

All analyses will be prepared on the AMS by treatment group, unless specified otherwise.

The following summaries of ADAb data will be prepared by treatment group:

- Summary table displaying the number and percentage of study participants with ADAb sample status (positive, negative, total of positive and negative, missing) at each visit, and overall ADAb status during the respective treatment periods of interest (overall up to Week 16 and Week 32 and separately overall up to Week 16 and Week 32 for the efficacy subgroup analysis). If $\geq 95\%$ of study participants are in the nonmissing groups, the missing group will not be displayed.
- Number and percentage of study participants with first occurrence of ADAb-positive result by visit by ADAb category:
 - Any ADAb-positive: ADAb-positive sample regardless of category during the treatment period
 - Category 7: Total treatment-emergent ADAb positive (combination of categories 2 and 5 [PreADAb negative – treatment-emergent ADAb-positive; and PreADAb-positive – treatment emergent ADAb boosted positive, respectively])

Study participants who are either treatment-emergent ADAAb positive or treatment-boosted ADAAb-positive for the first time at the specified time point in the study and the cumulative number and percentage of study participants with any ADAAb-positive sample and treatment-emergent ADAAb-positive and treatment boosted ADAAb-positive results at each time point will be summarized.

- Number and percentage of study participants in each of the 9 ADAAb categories (as defined in Section 4.6.1.4.1.4) up to Week 32 (repeated including SFU in the final analysis).
- All individual study participant-level ADAAb results will be listed including the screening assay, confirmatory assay, ADAAb sample status, and titers if applicable. Note that titer results will only be available if the confirmatory assay is positive. The listing will also include flags and reasons for exclusion for ADAAb measurements that are excluded from the by-visit summaries, as well as information on whether the bimekizumab concentration exceeded the ADAAb assay drug tolerance limit.

The following summaries of NAb data will be prepared by treatment group:

- Number and percentage of participants by the NAb categories (as defined in Section 4.6.1.4.1.6) during the respective treatment periods of interest (up to Week 16 and up to Week 32, repeated including SFU in the final analysis). These NAb summary tables will be repeated with percentages based on the total number of ADAAb-positive participants in each treatment group (thus, the ADAAb-negative group will not be displayed in this table).

4.6.1.4.2.2 Pharmacokinetics by ADAAb and NAb summaries

The following summaries of ADAAb data will be prepared by treatment group:

- Summary table displaying bimekizumab plasma concentrations by cumulative ADAAb sample status (positive, negative, missing) and visit during the respective treatment periods of interest from Baseline up to Week 32.
- Figures displaying geometric mean bimekizumab plasma concentrations by cumulative ADAAb status (ADAAb-negative, ADAAb-positive) over time during the respective treatment periods of interest from Baseline up to Week 32. SFU samples will not be included.

The following summaries of NAb data will be prepared by treatment group:

- Summary table displaying bimekizumab plasma concentrations by overall NAb status at Week 32 (ADAAb-negative, ADAAb-positive/NAb-negative, NAb-positive, and NAb missing) and visit during the respective treatment periods of interest from Baseline up to Week 32.

- Figures displaying geometric mean bimekizumab plasma concentrations and overall NAb status at Week 32 (ADAb-negative, ADAb-positive/NAb-negative, NAb-positive) over time during the respective treatment periods of interest from Baseline up to Week 32. SFU samples will not be included.

4.6.1.4.2.3 Efficacy endpoints by ADAb and NAb summaries

The following summaries of ADAb data will be prepared by treatment group:

- Number and percentage of PASI90 responders at Week 16 and at Week 32 by ADAb status. This will be repeated for IGA 0/1 responders at Week 16 and Week 32. These data will also be presented graphically.
- Number and percentage of PASI90 responders over time (up to Week 16 and Week 32) separated by overall ADAb status (up to Week 16 and Week 32, respectively). This will be repeated for IGA 0/1 responders (up to Week 16 and Week 32). These data will also be presented graphically.
- Number and percentage of PASI90 responders at Week 16 and Week 32 as a function of Week 16 and Week 32 ADAb titer categories (categorized as ≤ 100 [at or below the MRD of the assay], $>100 - < \text{median}$ [of non-missing titer values >100], and $\geq \text{median}$ [of non-missing titer values >100]). This will be repeated for IGA 0/1 responders at Week 16 and at Week 32. These data will also be presented graphically (for the figure, any study participant with ADAb-positive/ADAb titer missing is included ≤ 100 group).
- Individual plots of bimekizumab concentrations, ADAb titer, and PASI90 response (based on NRI) will be created. All 3 endpoints will be plotted on the Y-axes by time (X-axis) for the full treatment period including SFU. Plots will be labeled and grouped into the 7 predefined ADAb categories (category 1, 2, 3, 4, 5, 6, and 9).

The following summaries of NAb data will be prepared by treatment group:

- Number and percentage of PASI90 responders at Week 16 and at Week 32, by NAb category (ADAb-negative, NAb-positive, ADAb-positive / NAb-negative). This will be repeated for IGA 0/1 responders. These data will also be presented graphically.
- Number and percentage of PASI90 responders over time (up to Week 16 and Week 32) separated by NAb category (ADAb-negative, NAb-positive, ADAb-positive/NAb negative). This will be repeated for IGA 0/1 responders (up to Week 16 and Week 32). These data will also be presented graphically.

4.6.1.4.2.4 Safety endpoints by ADAb and NAb summaries

Summaries include the number of TEAEs, number of study participants with TEAEs, percentage of study participants with TEAEs, EAIR with 95% CI, and EAER. TEAEs will be sorted by SOC, HLT and PT.

TEAEs by ADAb status and ADAb titer:

TEAEs of the study participants initially randomized to bimekizumab 320mg Q4W/Q8W treatment, or initially randomized to placebo and initiating bimekizumab 320mg Q4W treatment at Week 16, will be summarized by ADAb status based on all available data using the following categories:

- AEs starting before the first ADAb-positive result (study participants in Categories 2 and 5)
- AEs starting on or after the first ADAb-positive result (study participants in Categories 2, 3, 4, 5 and 6)
- AEs for study participants who are always ADAb-negative (study participants in Category 1)

For these summaries, a study participant's associated time at risk will be split into the time before the first positive result and on or after the first positive result. If a study participant has multiple reports of the same AE (ie, those which coded to the same PT) emerging both prior to first ADAb-positive result and after ADAb-positive result, both events will be summarized in the table in the appropriate column.

In addition, for ADAb-positive study participants, a table summary of TEAEs by tertiles of maximum ADAb titer value will be generated. The table will display the summary of TEAEs which start on or after the first ADAb-positive sample by subgroups based on the tertiles of ADAb titer. For this summary, a study participant's associated time at risk will be based on the time on or after the first positive result.

TEAEs by NAb status:

TEAEs will be summarized by NAb status based on all available data using the following categories:

- ADAb-negative
- ADAb-positive/NAb-negative
- NAb-positive

